### Specific Objectives:

- Describe the sociodemographic, anthropometric, clinical and spirometric characteristics of the study participants.
- Determine the global and regional pulmonary impedance through the EIT during the use of the IMP.
- Determine the global and regional pulmonary impedance through the EIT during the use of the Triflo II®.

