### Main variables:

- EELI Delta ( $\Delta$ EELI): Measures the change in the average end-expiratory pulmonary impedance before and after an intervention.
- MTV ROI: Minute regional tidal variation

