### **Moments of electrical impedance tomography measurement**

Once the patient is connected to the tomograph, the quality of the signal must be checked. Once it is verified that it is being measured properly, that the patient is well positioned and that the signal is of high quality, the recording will begin. tomograph record; after the first

two minutes of calm breathing have elapsed, the first event will be marked, which will be recorded as "pre", and the use of the corresponding respiratory incentive will begin. The proper use of the device will be previously explained to you through a video that will illustrate the correct way to use it. The participant will receive visual feedback from the device when the condom is raised within the buretrol in the case of the IMP or when the spheres are raised in the branded incentive "Triflo II®"

Three series of ten breaths will be performed, with a 1-minute rest between series. In the last repetition of the third series, the second event will be marked, which will be recorded as "intra".

The maneuver will be finished once the series and repetitions are finished, removing the mouthpiece from the participant's mouth and they will be asked to continue breathing calmly for 2 minutes, after which the third event will be marked, which will be recorded as "post". And the recording of the record will be terminated.

At the beginning and at the end of the intervention, clinical data will be taken (heart rate, respiratory rate and oxygen saturation) and 15 minutes after finishing the test.

Taking into account that the subjects are using a device that is not used routinely in daily life, the perception of the subject in the use of each of the devices will be evaluated to know the degree of comfort of these by means of the scale of Likert and in the same way it will be valued if I generate perception of dyspnea by means of the Borg scale

The session may be interrupted if the participant does not wish to continue with the intervention, if the participant shows intolerance to the maneuver, if the respiratory rate is greater than 25 breaths per minute and if there is use of accessory muscles.

After each measurement is finished with each participant, the equipment will be disinfected

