## **Phase 4: Statistical analysis**

### Descriptive Analysis

The registration of the information will be carried out in the data collection formats designed for this purpose. To then be organized in the Microsoft Excel program. In order to have an initial knowledge of the behavior of each of the variables.

Quantitative variables will be presented as mean and standard error, and qualitative variables as frequencies and percentages. Normality tests (D'Agostino Pearson) will be applied to identify data distribution; subsequently, a paired T test will be performed to identify if the changes obtained after the interventions are statistically significant ( $p$  less than 0.05). For the statistical procedure, GraphPad Prism version 7.0 will be used.

For the EIT data, the monitoring sessions will be recorded with the participant's code, each recording will be transferred to a USB to be downloaded to the equipment where the information collected is stored for the reconstruction of the impedance measurement through the tool (Electrical Impedance Tomography Data Analysis Tool v6.3, Dräger Medical). This Reconstruction will allow us to isolate the main areas of interest (EIT measurement times) and quantify the percentage changes in EELI in response to lung expansion with respiratory incentive.

Anexo 1. Approval by a human subjects protection review board

Proyecto: **“DISTRIBUCIÓN DE LA VENTILACIÓN PULMONAR CON EL INCENTIVO MODIFICADO DE PACHÓN VS OTRO INCENTIVO RESPIRATORIO COMERCIAL, A TRAVÉS DE TOMOGRAFÍA DE IMPEDANCIA ELÉCTRICA, EN POBLACIÓN SANA DE LA CIUDAD DE CALI”**

Investigador Principal: **“[name]/ [name]/ [name]”**

Código Interno: (031-022)

Fecha en que fue sometido:

DIA	MES	AÑO
16	05	2022

El Consejo de la Facultad de Salud de la Universidad del Valle, ha establecido el Comité de Ética en Investigación en Salud (CEIS), el cual está regido por la Resolución 008430 del 4 de octubre de 1993 del Ministerio de Salud de Colombia por la cual se establecen las normas científicas, técnicas y administrativas para la investigación en salud; los principios de la Asamblea Médica Mundial expuestos en su Declaración de Helsinki de 1964, última revisión en 2013; y el Código de Regulaciones Federales, título 45, parte 46, para la protección de sujetos humanos, del Departamento de Salud y Servicios Humanos de los Institutos Nacionales de Salud de los Estados Unidos 2000. Este Comité certifica que:

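### No primary comparison is named among two main variables, global and regional readings and three marks, so nothing fixes which unadjusted test at 0.05 decides whether the devices are similar

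*Combined protocol and SAP*

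**What the plan says.** Five parts of the combined protocol and SAP bear on this point.

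- **Main variables** lists two items and ranks neither. The first is delta EELI, described as follows: "Measures the change in the average end-expiratory pulmonary impedance before and after an intervention". The second is "MTV ROI: Minute regional tidal variation".
- **Specific Objectives** includes "Determine the global and regional pulmonary impedance through the EIT during the use of the IMP", and the same aim is set for the Triflo II.
- **Moments of electrical impedance tomography measurement** marks three events in each session: pre, intra (last repetition of the third series) and post (after two minutes of quiet breathing).
- **Descriptive Analysis**, under Phase 4, has the only inferential statement: "a paired T test will be performed to identify if the changes obtained after the interventions are statistically significant", with p "less than 0.05". The only EIT quantity it names is the percentage change in EELI.
- **Null Hypothesis** and **Alternate Hypothesis** set up a single conclusion. The null is that the two distributions of ventilation are not similar, and the alternative is that they are.

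The supplied text gives no primary variable, region, mark or contrast, no number of regions, no adjustment for multiple tests, and no rule for combining several results into the one conclusion.

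**The concern.** One yes/no conclusion is to be drawn from a set of possible comparisons that the plan leaves open. Two errors follow, in opposite directions.

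1. If any significant between-device difference is read as not similar, then two identical devices fail by chance more often than 5% of the time once more than one comparison is tested.
2. If any variable or region that looks similar is taken as enough, a false claim of similarity becomes more likely for the same reason.

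Because the choice of variable, region and mark is not fixed in advance, it can also be made with the results in view. A reader of the final report could not then tell a planned result from a selected one.

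**Working it through.** The documents state no family-wise error rate, number of tests or power basis, so there is no figure of the plan's own to reproduce.

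**Inputs from the documents**
- Level per test: 0.05 (Descriptive Analysis). Sidedness is not stated; two-sided is assumed.
- Participants: 18, each using both devices (Population Sample; Study Design), so a paired t test has 17 degrees of freedom.
- Main variables: 2. Marks: 3, giving up to two changes from pre.

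**Assumptions, not in the documents**
- Every test compares IMP with Triflo II.
- The number of such tests, k, lies between 2 and 12. For example, 2 variables × 3 areas (global plus two regions) × 2 changes from pre = 12. A global reading of the second variable is itself an assumption, since it is defined regionally.
- The correlation between tests lies between 0 and 0.8.

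**Independent tests.** The chance of at least one p < 0.05 when the devices are identical is 1 − 0.95^k:
- k = 2: 1 − 0.9025 = 9.8%
- k = 4: 1 − 0.8145 = 18.5%
- k = 6: 1 − 0.7351 = 26.5%
- k = 12: 1 − 0.5404 = 46.0%

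**Correlated tests.** These come from simulated paired t tests with n = 18, two-sided 0.05, equal correlation between all pairs of tests, no true difference, and 20,000 runs per cell:

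| k | correlation 0.5 | correlation 0.8 |
|---|---|---|
| 2 | 9.1% | 7.9% |
| 4 | 15.9% | 12.1% |
| 6 | 21.6% | 14.2% |
| 12 | 32.8% | 19.4% |

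Two tests therefore give about 8–10%. Four to 12 tests give about 12% (k = 4, correlation 0.8) to 46% (k = 12, independent). Wider assumptions, 2 to 20 tests and correlation 0 to 0.9, give about 7% to 64%.

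**The opposite error.** Suppose similarity were tested against a margin of 0.75 SD at one-sided 5%, the true difference sat exactly at the margin for all of 7 comparisons, and any one pass were enough. The simulated rate of a false similarity claim is then about 30%, 21% and 14% at correlation 0, 0.5 and 0.8. The margin, the count and the any-pass rule are all assumptions, and placing every comparison at the margin is the worst case. The result shows only the direction and rough scale.

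**With the change.** One pre-stated comparison at 0.05 carries a 5% risk. Splitting 0.05 equally instead would need 0.05/2 = 0.025 per test for two tests and 0.05/12 = 0.0042 for 12.

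**The case against.** The strongest reply is that the plan does not commit to a large family of tests.

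- **Scope of testing.** Descriptive Analysis has one generic sentence, the objectives are worded as estimation for each device separately, and the marks are recording events rather than declared endpoints. This stands: a reader might infer that every variable-region-mark combination is tested at 0.05, but the documents do not say so. They do not exclude it either, and that open choice is the problem.
- **Which contrast.** The quoted test may be a pre-post test within each device. This also stands. The percentages above apply only to IMP versus Triflo II tests. If the within-device reading is the intended one, the quoted sentence supplies no test of the general objective, which is a comparison of the devices.
- **Within-device tests as an added risk.** A reader might think that pre-post tests within each device add to the risk of a false difference between devices. They do not. If an incentive changes impedance, those null hypotheses are false and a significant result is correct.
- **Type of error.** Similarity is the alternative hypothesis, so a chance difference is not a type I error of the trial's own hypothesis. It is a false failure to show similarity. The inflation is real, but should be described that way.
- **Dependence.** If regional values were shares of a total, two regions would give the same two-sided p value and count as one test. The documents do not say how they are expressed, so the effective number of tests may be smaller than a simple count.
- **Unseen material.** The EIT operating procedure (SOP 3) is not reproduced and may define the regions, and part of the document was not available for review. Absence is claimed only for the supplied text.

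**Conclusion.** The point holds in conditional form. The supplied text does not fix which result decides the similar/not-similar verdict, and it has no multiplicity rule. If several between-device tests are run at 0.05 and the devices are identical, the chance of at least one false difference is about 8–10% for two tests and about 12–46% for 4 to 12 tests. This rests on two-sided paired t tests with n = 18 and an assumed correlation of 0.8 down to 0.

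A reader might attach one unconditional figure, for instance 15–49%. That range needs an assumed 7 to 13 tests as well as assumed correlations, and it leaves out the case in which only the two main variables are compared once each. The documents do not support it as a property of the plan. The case for a change does not depend on the exact figure, because even two tests come close to doubling the 5% level and the post-hoc choice of result remains open.

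Nor would naming one difference test at 5% settle the hypotheses by itself. A non-significant difference does not establish similarity, and the plan gives no margin.

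**What to change.** Amend Main variables and Descriptive Analysis before any data are seen.

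1. **Name one primary comparison:** the within-participant IMP minus Triflo II difference in one main variable, one region or index, and one mark. The regional ventilation variable at the intra mark is one candidate, because the general objective concerns ventilation during use.
2. **State how it decides.** Report the difference with its confidence interval, and let this comparison alone inform the hypotheses. Judge it for similarity against a margin that the sponsor states and justifies in advance, not by a non-significant p value.
3. **Treat everything else as secondary.** Report the other variable-region-mark results as estimates with 95% intervals and no significance claim, or adjust them by Holm's method.
4. **If similarity is wanted in every region,** say that all regions must meet the margin. As a set of equivalence tests this needs no alpha adjustment, but it costs power with 18 participants. The same exemption does not apply to ordinary difference tests.

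**Cost.** No extra participants or measurements are needed for the named comparison. The text changes are short, but choosing and justifying a margin is real work, and the power at n = 18 should be checked against it. The other main variable and the remaining regions lose stand-alone significance claims.

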## Methods

### Study Design

Crossover clinical trial, in which the measurement of the distribution of pulmonary ventilation by means of EIT will be evaluated, during the use of a Branded flow respiratory incentive “Triflo II®” and the IMP, in a sample of healthy volunteers from the city of Santiago de Cali. Both incentives will be used on all participants, and the order of assignment will be randomized.

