### Population Sample

Sample size of 18 subjects (9 men, 9 women) healthy volunteers from the Municipality of Santiago de Cali. The type of sampling will be non-probabilistic for convenience.

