### **Randomization**

The randomization to choose which will be the first incentive that each participant will use and to which the first ventilation measurement will be carried out by means of EIT, will be carried out by simple randomization, through the "RANDOM.ORG" program (<https://www.random.org/lists/>) and <http://www.jerrydallal.com/random/permute.htm>

These measurements will be made at the facilities of the Universidad del Valle, according to availability. The first measurement will be carried out with the incentive that has been randomly assigned to the participant, the second measurement will be carried out one week after the first measurement was made with the other incentive, with the objective that the washing period is fulfilled, both measurements will be performed by the principal investigator. For the measurement of the EIT, the instructions defined in standard operating procedure 3 will be followed and for the application of the protocol for the use of incentives, the instructions defined in standard operating procedure 6 and 7 will be followed according to the corresponding incentive. The duration of this procedure will be approximately 30 minutes for each measurement.

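### The plan does not fix the scale on which the EELI change is tested, and it leaves each session's own pre value unused as a covariate

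*Combined protocol and SAP*

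**What the plan says.** Delta EELI is one of two main variables. The Main variables section describes it in words only: "Measures the change in the average end-expiratory pulmonary impedance before and after an intervention". It gives no units, formula or denominator.

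The analysis is in Phase 4, Descriptive Analysis. There "a paired T test will be performed to identify if the changes obtained after the interventions are statistically significant", with p "less than 0.05". A separate paragraph on reconstructing the EIT recordings says the tool will serve to "quantify the percentage changes in EELI in response to lung expansion with respiratory incentive".

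The design is a crossover: "Both incentives will be used on all participants, and the order of assignment will be randomized". The Randomization section adds that "the second measurement will be carried out one week after the first measurement was made with the other incentive", so every participant has a separate pre value for each device. The section on moments of EIT measurement marks three events (pre, intra and post). The first comes once "two minutes of calm breathing have elapsed, the first event will be marked, which will be recorded as 'pre". The Population Sample section gives "Sample size of 18 subjects (9 men, 9 women) healthy volunteers from the Municipality of Santiago de Cali".

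**The concern.** Three things are left open for a main variable.

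- **Scale.** A reader of the Main variables section would probably test post minus pre in impedance units. A reader of the reconstruction paragraph would probably test a percentage of the pre value. These are different quantities whenever pre values differ between people or sessions.
- **Time pair.** The variable's definition suggests pre to post. The General Objective concerns ventilation while the device is in use, which suggests pre to intra.
- **Contrast.** The test sentence allows a before-after test within each device as well as a comparison between devices. Only the second addresses the General Objective.

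With 18 pairs, a choice made after the data are seen can decide whether a result is called significant. The plan also collects a pre value in every session and, as far as the text shows, uses it only to form the change.

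**Working it through.** **1. The plan's own figure.** The sample size of 18 comes with no effect size, SD or power, so no power calculation can be reproduced. It does equal the age-by-sex grid: 3 age bands x 2 sexes x 3 people = 18. For a paired t test with n = 18 and two-sided 0.05 (sidedness is assumed), the detectable standardized paired difference is 0.70 for 80% power and 0.81 for 90%.

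**2. The scales can differ in direction.** Suppose nine people have pre value 50 (device A +20, device B +10) and nine have pre value 200 (A +40, B +60).
- Raw means: A (20 + 40)/2 = 30; B (10 + 60)/2 = 35. B is higher.
- Percentage means: A (40% + 20%)/2 = 30%; B (20% + 30%)/2 = 25%. A is higher.
- The paired t statistics for B minus A are +1.37 and -1.37, both p = 0.19. The direction flips, but neither result is significant.

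**3. Which scale has more power.** The assumptions are a mean pre value of 100, lognormal pre values, and a device difference set to give 80% power on the scale that matches the data (40,000 trials per scenario). Entries are power for raw / percentage change.

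| Baseline CV, between-session correlation | Change unrelated to baseline | Change proportional to baseline |
|---|---|---|
| 0.1, 0.9 | 80% / 79% | 79% / 80% |
| 0.2, 0.5 | 80% / 74% | 74% / 80% |
| 0.3, 0.5 | 80% / 67% | 67% / 80% |
| 0.5, 0.5 | 80% / 51% | 51% / 80% |
| 0.8, 0.5 | 80% / 33% | 32% / 80% |

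The loss is symmetric: whichever scale does not match the data loses power.

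**4. How often the choice matters.** The second set of assumptions is a device effect of 6 on a pre mean of 100, session SD 8, measurement SD 6 at pre and at post, and baseline CV 20-50%. Noise is either constant or scaled to the person's level (8% and 6%).
- Constant noise: power 49-52% for raw change and 31-49% for percentage change.
- Proportional noise: 43-51% for raw change and 49-65% for percentage change.
- The two scales disagreed on p < 0.05 in 7-21% of trials.
- Point estimates had opposite signs in 1-7% of trials.

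**5. What the pre value adds.** Take the raw scale with constant noise.
- Unadjusted: the variance of the device difference in change is 4 x 6^2 = 144, so the SD is 12 and the standardized effect is 6/12 = 0.50.
- Adjusted: the pre difference and the post difference each have variance 2 x (8^2 + 6^2) = 200, and their covariance is 2 x 8^2 = 128. The residual variance is 200 - 128^2/200 = 118.1, so the SD is 10.9 and the standardized effect is 6/10.9 = 0.55.
- Simulated power agrees: about 52% unadjusted and 57% adjusted.

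Across scenarios, on a matched scale, adjustment gained about 3-8 points when session levels varied modestly. When session levels vary a lot, the slope approaches one, adjustment reproduces the simple change, and only the lost degree of freedom is felt: at most about 2 points.

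**6. Bias of a mean percentage.** With no true change and independent lognormal errors, the expected percentage change is exp(s^2) - 1 with s^2 = ln(1 + CV^2), which equals CV^2. That is 1%, 4% and 9% for measurement CVs of 10%, 20% and 30%. At the noise used in step 4 it is 0.06^2 = 0.36%, and simulation gave 0.3-0.9%.

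**The case against.** The strongest reply is that the two sections do not conflict. The variable's definition says change and does not exclude a percentage, so the reconstruction paragraph may only say how that change is expressed. The percentage wording also sits apart from the test sentence. This stands: the text shows an unspecified scale, not a demonstrated mismatch between a defined and an analysed outcome.

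A reader might infer three stronger things.
- **Percentage change is the less efficient choice.** Steps 3 and 4 show that this follows from assuming an effect or noise that does not grow with baseline. Under the opposite assumption percentage change does as well or better. The documents give no EELI mean, SD or noise level.
- **The scale can reverse the device conclusion.** Opposite signs are possible but uncommon when a real difference exists (0-6% in the step 3 simulations, 1-7% in step 4). Disagreement about significance is the commoner risk, and it is not a reversal.
- **Percentage change is materially biased upward.** At the noise level assumed for power the bias is below 1%, and it largely cancels between devices when noise is equal. It would matter for a within-device test with much noisier readings. The wording allows such a test, but the documents do not show such noise.

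It can also be said that raw units may not be comparable across sessions a week apart, which makes normalising to the session's pre value defensible. That is fair, and it is why raw units should not be imposed. A log-scale analysis adjusted for log pre meets the point, because the log ratio is its special case with slope one.

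**Conclusion.** The point holds as a specification gap with a cheap gain in efficiency. Scale, time pair and contrast are open for a main variable. The choice between raw and percentage change decided significance in about 7-21% of simulated trials. The documents do not show percentage change to be inferior and do not settle which scale is right.

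Separately from that choice, adjusting for the session's pre value is worth having: about 3-8 power points gained when session levels vary modestly, at most about 2 lost otherwise.

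All of these sizes rest on assumed values: baseline CV 20-50%, a 6-unit effect on 100, the stated session and measurement noise, and two-sided testing. The qualitative conclusion does not depend on the particular values.

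**What to change.** In the Main variables section and in Phase 4, Descriptive Analysis:

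1. Name one scale for delta EELI, raw or log ratio, and one time pair (pre to post or pre to intra), before any trial data are analysed. Recordings from the five pilot subjects, who are outside the sample, could be inspected for whether change and noise grow with level, though five people cannot settle it.
2. Replace the paired t test on unadjusted changes with a device-versus-device comparison. Take each person's post values on the chosen scale (intra values if that pair is chosen), form the difference IMP minus Triflo II, and regress it on the same person's difference in pre values on that scale. The intercept, with its confidence interval, is the device difference at equal pre values.
3. Report percentage change descriptively or as a sensitivity analysis.

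This is a free to cheap improvement. It takes a few sentences and no new measurements, and it costs one degree of freedom (16 residual instead of 17). If the log scale is chosen, the result is a ratio and can be back-transformed to a percentage for readers.
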